Preoperative anxiety is a common occurrence for many patients undergoing all types of surgery.^{1,2} Patients with a high level of anxiety before surgery have been shown to have numerous negative outcomes both intra-operatively and post-operatively.³⁻¹⁰ Many studies have shown that preoperative psychological interventions that aim to reduce anxiety also result in improved post-operative behavioral and clinical recovery.⁸ Currently, the most common method to treat preoperative anxiety is the administration of a prescription benzodiazepine.¹¹ However, there is limited clinical evidence that supports the use of sedative premedication, such as with a benzodiazepine, before surgery.¹² Complementary integrative medical therapies including music, massage, guided imagery, and deep breathing have been proposed to minimize stress and pain in surgical patients.^{13,14} These therapies are thought to be effective by evoking the relaxation response through stimulation of the parasympathetic nervous system and engagement of the patient in the healing process.¹⁴ Relaxation and deep breathing, particularly, have been shown to reduce pain, anxiety, and “tension-anxiety” in hospitalized patients.^{14,15} Based on this evidence, a guided paced deep breathing module has been proposed to reduce preoperative anxiety in patients undergoing gynecological surgery at Mayo Clinic Rochester Methodist Hospital. In this study, patients’ anxiety will be assessed pre-intervention on a 0-10 numeric rating scale, as well as post-intervention and a paired t-test will be used to assess effectiveness. Additionally, qualitative questions will be administered via a questionnaire post-intervention to gain more insight on the effectiveness of the intervention. The feasibility of the intervention in the busy preoperative setting will be evaluated by assessing how many times a patient is interrupted while participating in the paced deep breathing module. If this module is found to be effective in reducing patients’ anxiety, it will be implemented into practice so that every patient is offered the module preoperatively.

Research Plan

I. Background and Significance:

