Based on this evidence, an electronic paced deep breathing module has been proposed to reduce preoperative anxiety in patients undergoing gynecological surgery at Mayo Clinic Rochester Methodist Hospital. The gynecological surgery population has been selected because of research suggesting women tend to have a higher level of anxiety before surgery and may be more receptive to relaxation exercises.¹⁶⁻¹⁸ Additionally, women undergoing gynecological surgery were found to have an average anxiety rating of four on a zero to ten numeric rating scale.¹⁷

II. Purpose of the Study:

The purpose of this study is to evaluate the effectiveness of an electronic guided paced deep breathing module implemented into the preoperative setting of gynecological surgery to reduce patient anxiety. If this intervention is found to be effective, we plan to implement into practice the paced deep breathing module that every patient is offered preoperatively.

III. Specific Aims of the Study:

Primary Aim: The study’s primary aim is to assess if utilizing an electronic paced deep breathing module administered in the preoperative setting can decrease a patient’s anxiety level prior to undergoing gynecological surgery. This study will determine if more research is needed or if the results are overwhelmingly positive in reducing anxiety, we plan to implement into practice the paced deep breathing module that every patient is offered preoperatively.

Secondary Aim: The secondary aim of this study is to collect qualitative data regarding patient satisfaction with the paced deep breathing module.

Tertiary Aim: The tertiary aim of this study is to evaluate the feasibility of implementing a paced deep breathing module into the busy preoperative setting of gynecological surgery.

Hypothesis: In adult females undergoing gynecological surgery, the use of a preoperative electronic guided paced deep breathing module will decrease anxiety levels.

IV. Literature Review:

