Additionally, the Neuman Systems Model can be applied. "The Neuman Systems Model is a systemic perspective of health and wellness, defined as the condition or the degree of system stability, that is, the condition in which all parts and subparts (variables) are in balance or harmony with the whole of the client/client system."^{27, p.12} The model is based on the individual's continuous relationship to environmental stress factors. These environmental stress factors have the potential to cause a reaction or a symptomatic reaction to stress thus affecting the client's current health status.²⁷ This model relates to the present study in that the patient is being treated in a holistic manner on the basis that anxiety before surgery has negative outcomes both intra-operatively and post-operatively, thus preoperatively treating the patient's anxiety with the deep breathing module will, in turn, positively benefit the patient's health status.

VI. Significance:

Guided deep breathing has been found to be effective in reducing patient anxiety in the hospital setting, including during the preoperative period. However, this will be the first study to implement a guided deep breathing focused intervention into the *immediate* preoperative period for gynecological surgery patients to determine its effectiveness on reducing anxiety and evaluate patient satisfaction. Currently, gynecological surgery does not offer any such intervention. This will be the first approach to reduce patients' preoperative anxiety with a deep breathing intervention. This study has the potential to significantly add to the evidence and literature supporting the potential benefits of paced deep breathing exercises in the immediate preoperative setting. It will also provide a baseline for continued research on the benefits of paced deep breathing utilized in the immediate preoperative setting in specialty practices other than gynecological surgery.

VII. Methods:

This is a study with a pre- and post-test quasi-experimental design. This study will specifically examine an electronic paced deep breathing module for adult female patients undergoing gynecological surgery in the preoperative setting. This pre/post-test design was chosen to measure the primary outcome of anxiety level and gain patient's feedback on the module, as well as evaluate the feasibility of implementing the module into the busy preoperative setting of gynecological surgery.

a. Subjects and setting:

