The study will be offered to a convenience sample of 45 adult female patients in the preoperative area of gynecological surgery on Eisenberg 1-4 at Mayo Clinic Rochester Methodist Hospital. This unit has approximately ten private rooms where patients are called from the outpatient AM admit area or hospital room to be evaluated and wait until called into the operating room for surgery. All patients undergoing gynecological surgery pass through this unit. According to nurses working on Eisenberg 1-4, the average length of stay in these rooms is about one hour.

All patients recruited will be assigned to the intervention group, as there is no control group. The sample size for this investigation was determined for the primary outcome of anxiety assessed pre- and post-intervention. From previous investigations which have assessed interventions aimed at reducing anxiety in surgical patients, the magnitude of the effect (i.e. change in anxiety expressed in SD units), has ranged from 0.5 to 0.9.^{18,19} In general, for a one-sample study a sample-size of N=45 will provide statistical power (two-tailed, alpha=0.05) of 90% to detect a change of 0.5 SD. Therefore a sample-size of N=45 is proposed.

Inclusion Criteria: Women aged 18 years or older undergoing gynecological surgery on Eisenberg 1-4; English-speaking; Able to complete pre- and post-intervention questionnaires; Able to read and understand informed consent form

Exclusion Criteria: Non-English speaking women; first-case of the day gynecological surgery patients

b. Instruments and Data Collection (See Appendix):

1. Rapid Anxiety Assessment Tool (RAAT) 0-10 numeric rating scale
2. Qualitative questions regarding paced deep breathing module
3. Demographic data collected on pre-intervention survey

Baseline anxiety will be assessed upon admission to Eisenberg 1-4 using the Rapid Anxiety Assessment Tool (RAAT) zero to ten numeric rating scale and demographic information will be collected. This tool has been validated in the literature and is a single-item numeric rating scale that provides a quick assessment of patients' anxiety level.¹⁷ The tool rates anxiety on a zero (no anxiety) to ten (worst anxiety possible) numeric scale and is easy for patients to use.¹⁷ The tool additionally has been correlated with Spielberger's State-Trait

Anxiety Inventory-State Scale with $r=0.77$ validity in a sample of 197 patients evaluated in the preoperative period.¹⁷

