Demographic data for the study population will be collected on the pre-intervention questionnaire including age, diagnosis, type of surgery, and whether the patient has utilized deep breathing or meditation exercises within the last twelve months. After the intervention, anxiety will be assessed again using the RAAT numeric rating scale and qualitative questions regarding the module will be assessed. Data will be collected from paper questionnaires.

Feasibility will be assessed by determining if and how many times each patient was interrupted while using the paced deep breathing module.

c. Procedures:

Patients will be recruited by primary investigators, [name], SRNA, and [name], APRN, CNS, D.N.P., as well as co-investigator, [name], by the assistance of a research flyer (see appendix). Additionally, a surgical listing of patients undergoing gynecological surgery for each day will be obtained by the primary investigators or co-investigator. Inclusion/exclusion criteria will be evaluated to determine eligibility and eligible patients will be approached by the primary investigators/co-investigator and asked if one is interested in participating in a deep breathing/meditation intervention. The primary investigators/co-investigator will then provide information and instruction regarding the questionnaires and intervention module to the patient. The patient will then be asked for verbal consent and written signed HIPAA authorization to participate. Once consent is obtained, the primary investigators/co-investigator will provide the patient with the questionnaire packet (including pre- and post-intervention questionnaires) as well as introduce and set up the module on an iPad or portable laptop for the patient. The paced deep breathing module consists of ten minutes of a guided breathing exercise while culminating a calm and energized mind. It was developed by [name], M.D. and is entitled “Calm and Energize: A Meditation with Your Breath.” The script for this meditation is led by [name] and is as follows:

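### Feasibility is measured only in women who start the module, completion is not reliably recorded, and VII.d names no feasibility analysis (tertiary aim only)

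*Combined protocol and SAP*

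**What the plan says.** Section III sets the tertiary aim as to "evaluate the feasibility of implementing a paced deep breathing module into the busy preoperative setting of gynecological surgery". The opening of Section VII repeats this among the reasons for the design: "evaluate the feasibility of implementing the module into the busy preoperative setting of gynecological surgery".

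The measure appears twice, in matching terms. The opening summary, before the Research Plan, says feasibility will be judged by "how many times a patient is interrupted while participating in the paced deep breathing module". Section VII.b says: "Feasibility will be assessed by determining if and how many times each patient was interrupted while using the paced deep breathing module".

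On recruitment, VII.a says "The study will be offered to a convenience sample of 45 adult female patients". VII.c adds that "a surgical listing of patients undergoing gynecological surgery for each day will be obtained", that eligibility is then checked, and that "eligible patients will be approached by the primary investigators/co-investigator". No count is requested at any of these steps.

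During the ten-minute module staff leave the patient alone, although family may stay, and a door card is used to limit interruptions (VII.c). The second anxiety score is nominally taken when the module ends, and a unit nurse collects the packet. Patients may stop early (VII.c, VIII.a). The text describes no record of early stopping.

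Section VII.d covers subject characteristics, the change in anxiety score, and content analysis of the post-intervention survey. It mentions neither feasibility nor interruptions.

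**The concern.** The aim concerns implementation, whereas the measure concerns what happens after implementation has already succeeded for a given woman. In a busy unit, one plain way to fail is that she is called to surgery before anyone can approach her, obtain consent and set up the device. Such women contribute nothing to the interruption count. The same count could therefore arise whether nearly all eligible women could start or many could not.

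A second gap follows. Among women who do start, the plan has no direct record of whether they finished. Third, with no feasibility analysis in VII.d, one of the three stated aims has no named summary.

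At stake is how the tertiary result is read. Few interruptions among users could be reported as showing that the module is feasible in this unit, when the result is conditional on having started. Counts not kept on the day may be impossible to reconstruct later.

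**Working it through.** **The plan's own figure.** No figure is given for feasibility. The only design calculation is for the primary outcome (VII.a): N=45, two-sided alpha 0.05, change of 0.5 SD, power 90%. For a one-sample t-test the noncentrality is 0.5 × √45 = 3.354 with 44 degrees of freedom, giving power of 90.7%. The stated 90% reproduces. Nothing below depends on it.

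**What the planned data can show, step by step.**

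| Step | Data source in the plan | Counted as written? |
|---|---|---|
| Eligible on the day | Surgical listing and eligibility check (VII.c) | Source exists; no count planned |
| Reached in time and approached | Investigators (VII.c) | No |
| Declined | Investigators (VII.c) | No |
| Started | Investigators set up the device (VII.c) | Not explicitly |
| Interrupted while using | VII.b | Yes, among starters |
| Completed | Post-module score (VII.c) | Only indirectly |

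**Starting.** Let E be the eligible women who could have been approached, S those who start, and I those interrupted at least once. The stated measure yields I/S and the distribution of interruption counts within S. Implementation also depends on S/E. I/S carries no information about S/E: with I and S fixed, E can take any value from S upwards. The documents give no E, so S/E cannot be computed or bounded from them.

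The only time figures are an average stay of about one hour by nurses' report (VII.a) and a ten-minute module (VII.c). On average that leaves 60 − 10 = 50 minutes for everything else. An average without a spread does not say how many women have too little time.

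**Completion.** Take each possible state of the post-module form:
- *Missing.* The woman may have been called to the operating room, may have chosen to stop, or may have finished and left the form blank.
- *Returned.* She probably finished, but a woman who stopped early can also fill in the form.

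Both states are ambiguous, so the number of returned scores is neither a lower nor an upper limit for the number who completed.

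**Precision of a descriptive summary.** Assume 45 starters (VII.a may mean fewer; see the verdict). The exact (Clopper-Pearson) 95% limits for x of n are the 2.5% point of Beta(x, n−x+1) and the 97.5% point of Beta(x+1, n−x). For the proportion interrupted, with assumed counts:
- 0/45: 0% to 7.9% (upper limit 1 − 0.025^(1/45) = 0.079)
- 9/45 = 20%: 9.6% to 34.6%
- 23/45 = 51%: 35.8% to 66.3%

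A sample of this size supports a useful description but not a precise estimate, which is a reason to report intervals.

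**Analysis.** VII.d does mention frequency counts and percentages, but for subject characteristics. The survey sentence refers to qualitative content analysis. Neither plainly covers interruptions, starting or completion.

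**The case against.** The strongest reply is that the plan defines its tertiary measure consistently in two places, that interruptions are a sensible concern in a busy unit, and that the door card addresses exactly that. On this view, wanting reach and completion as well is a broader idea of feasibility, not a correction. It stands in part: the measure is valid and should stay. But the plan's own aim is implementation in that setting, and a measure conditional on starting answers only part of it.

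Second, much is countable already. Consenting women sign an authorization, receive a packet and get a study code, and eligible women are on the daily listing. If 45 is literally the number offered the study, starters out of 45 follows. This is fair, and it is why the remedy is cheap. It still omits eligible women never approached for lack of time.

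Third, the gap in VII.d may be narrower than it looks. VII.b mentions paper questionnaires immediately before the feasibility sentence, and the appendix forms were not available for review. An interruption item there might fall under the survey summary. This also stands, but a patient form cannot count women who never received it.

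Fourth, the remedy is imperfect. The start proportion mixes routine feasibility with research consent and investigator availability, and the completion item relays the patient's report because nobody observes her. Both are true and should be stated with the results.

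**Conclusion.** The point holds as a cheap improvement to the tertiary aim. As written, the plan can say how often users were interrupted. It cannot say what share of eligible women could start, and it does not reliably say what share of starters finished. The primary analysis and its sample size are unaffected. The size of the gap is unknown, because it depends on counts that are neither given nor planned.

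The conclusion assumes that the appendix forms do not redefine feasibility, and it leaves open whether 45 means women offered the study or women recruited. The wording in VII.a fits the first; the power statement needs 45 women with both scores.

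A reader might infer more than the documents support:
- *That few women will be able to start.* No reach data are given. Any start percentage would rest on an invented denominator, so none is offered here.
- *That missing post-module scores bound the completion rate.* They do not, because an early stopper may still return the form.
- *That interruptions will go unanalysed.* An unseen survey item may cover them.
- *That the rollout decision rests on this measure.* The opening summary and Sections II and III tie rollout to reduced anxiety, not to feasibility.
- *That excluding "Non-English speaking women; first-case of the day gynecological surgery patients" is a further defect of the feasibility aim.* It limits whom the result describes, and VII.e already lists limited generalizability.

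**What to change.** 1. **Tally on recruiting days.** From the surgical listing and eligibility check already in VII.c, the investigators record counts without identifiers: eligible; approached; not approached, split into no time before transfer and investigator unavailable; declined; started.
2. **One item at packet collection.** For every packet, including unfilled ones, the nurse records whether the module was completed (yes/no, as reported by the patient). If not, the nurse records the reason: called to the operating room, patient choice, or other.
3. **A paragraph in VII.d.** Report, each with an exact 95% confidence interval:
   - started / (approached + not approached for lack of time), shown with and without research refusals in the denominator; investigator unavailability is shown separately and kept out of it;
   - completed / started.

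   Summarise interruptions among starters as the proportion interrupted and the distribution of counts.
4. **Two sentences of interpretation.** State that the start proportion also reflects research consent and investigator set-up, and that completion is reported, not observed.
5. **Clarify the 45 in VII.a:** women offered the study, or women recruited.

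The cost is a tally sheet, one item for the nurse, and a short addition to the text. No extra patients or staff are needed. The split between lack of time and investigator unavailability will rest on the investigators' own judgement.
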